Last Observation Carried Forward (LOCF) will be used for filling missing values.

Evaluation of sample size

Evaluation of sample size was based on the following rules and assumptions:

1. Statistical provisions.
 - 1.1 Power of statistical criteria " $P = (1 - \beta)$ " is considered to be equal to 80% (probability of correct rejection of null hypothesis is 0.8).
 - 1.2 Probability of error of the first kind " α " is admitted to be $< 5\%$ (probability of erroneous acceptance of alternative hypothesis is < 0.05).
 - 1.3 The statistical criteria used are two-sided.
 - 1.4 Calculation of total sample size was based on the assumptions on expected effects on primary endpoint claimed in the protocol.
 - 1.5 Effect of interim statistical analyses on probability of error of the first kind is regulated at each point (interim analysis, final analysis) using O'Brien-Fleming boundary.

2. Assumptions on expected clinical study effects.

It is assumed that the difference between average disease duration (until recovery or significant improvement) in Anaferon for children and Placebo groups will be less than 0.5 days, while standard deviation in both groups will not exceed 2 days.

Taking into account that statistical analysis will be performed twice – at interim analysis and at final analysis – based on the assumed effect the minimum required size of each group (product and placebo) will be as follows:

Number of subjects	Interim analysis	Final analysis
Number of subjects in both groups	254	508
including		
- number of subjects in Anaferon group	127	254
- number of subjects in Placebo group	127	254

Given withdrawal at screening, including due to negative rapid influenza test (the ratio is 1 subject with positive test/5-6 subjects with influenza-like symptoms and negative influenza test) and during the study, the final sample size will be 972 subjects to be enrolled.

This calculation is made using the formula: $N_T = N_{PP} / (1 - C_w)$, where N_T – final sample size; N_{PP} – scheduled number of subjects completing the study per protocol ($N_{PP}=508$); C_w – withdrawal coefficient ($C_w=0.4774$).

Interim analysis

Interim analysis of *Particular Per Protocol (pPP)* is scheduled within the study.

Purposes of interim analysis:

- Ability to adjust sample size in case in minor deviation of the effect achieved from the effect specified at baseline;

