- Ability of early discontinuation of the study in case of major deviation⁷ of the effect achieved from the effect specified at baseline.

Within the protocol one interim analysis point has been scheduled.

Interim analysis is scheduled for the time when at least 127 subjects in each group complete the study, i.e. receive per protocol therapy in full, undergo all scheduled visits and have no major protocol deviations.

Statistical criteria

All statistical calculations will be made using the following groups of statistical criteria:

- parametric – to assess continuous and interval accidental values;
- non-parametric – to obtain:

⁷ Early study termination is possible both on safety reasons in case of lack of efficacy and after the required power of statistical efficacy conclusions is achieved.

- evaluations on equality/inequality of proportions of subjects compared for various visits,
 - analysis of frequencies in features compared,
- and
- evaluation of continuous and interval accidental values in case of violation of requirement on normal sample distribution;
 - interim analysis procedures.

Parametric criteria will be checked for normalcy of the samples compared (Kolmogorov-Smirnov test).

The following *parametric methods and approaches* are suggested:

1. To evaluate various continuous variables obtained in two different (independent) groups – Student’s test for independent samples.
2. To evaluate differences in continuous variables obtained in one group at two different visits – Student’s test for paired samples.
3. For multiple assessment at different visits – Bonferroni’s test (Student’s test modification for multiple comparisons).
4. For comparison of several sample means with baseline (control) – Dunnett’s test (Student’s test modification for multiple comparisons with control).
5. For evaluation of time changes in parameters under comparison – analysis of variance (ANOVA, MANOVA) in modification with repeated measures.

To carry out the statistical analysis and approaches specified above the following SAS procedures are suggested:

- UNIVARIATE – check for normalcy of distributions compared;
- CORR, MEANS – calculation of descriptive statistics;
- TTEST – Student’s test with all modifications;
- GLM, GENMOD, GLIMMIX – analysis of variance (ANOVA/ANCOVA, MANOVA/MANCOVA).

Nonparametric criteria:

1. For evaluation of differences in continuous variables obtained in two various (independent) groups – Mann-Whitney test;

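### The interim may change the sample size on the achieved effect, but no re-sizing rule or matching final test is given, so alpha below 5% is not assured

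*Combined protocol and SAP*

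**What the plan says.** All references are to the Combined protocol and SAP, under Statistical Analyses unless stated.

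- **Alpha.** Evaluation of sample size, item 1.2: "probability of erroneous acceptance of alternative hypothesis is < 0.05". Item 1.3 makes the tests two-sided. Item 1.5 says the effect of interim looks on this error "is regulated at each point (interim analysis, final analysis) using O'Brien-Fleming boundary".
- **Assumed effect.** Item 2 of the same section takes a difference in mean illness duration of less than 0.5 days. The same sentence gives an SD of at most 2 days. The table gives 127 per group at the interim and 254 at the end, as minimum sizes.
- **Purposes of the interim.** The first is "Ability to adjust sample size in case in minor deviation of the effect achieved from the effect specified at baseline". The second is "Ability of early discontinuation of the study in case of major deviation" from the same baseline effect. Footnote 7 adds: "Early study termination is possible both on safety reasons in case of lack of efficacy", or once the required power is reached.
- **Timing.** "Interim analysis is scheduled for the time when at least 127 subjects in each group complete the study".
- **Tests.** Statistical criteria names Student's test ("To evaluate various continuous variables obtained in two different (independent) groups") and, among the nonparametric criteria, Mann-Whitney ("For evaluation of differences in continuous variables obtained in two various (independent) groups"). SAS SEQTEST is named for the interim.

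The text does not say what counts as a minor deviation, whether the size may rise, fall or both, what the largest size is, or how the final test allows for a changed size.

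**The concern.** A group-sequential boundary controls alpha because the weight of each stage in the final statistic is known in advance. If the second-stage size is chosen after seeing the first-stage difference, those weights become data-dependent. The pooled statistic then no longer has the null distribution from which the final critical value was computed. Choosing a larger second stage after a weak interim, or a smaller one after a strong interim, can each raise the chance of a false positive. Naming O'Brien-Fleming or SEQTEST does not close this gap, because adjusting a boundary for a changed information level assumes that the change did not depend on the observed effect.

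At stake is the primary efficacy claim. After a re-sizing, the sponsor could not show from this text that the stated 5% still applies.

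**Working it through.** **Inputs.** From the plan: alpha 0.05 two-sided, power 80%, SD 2, difference 0.5 day (the text says less than 0.5; 0.5 reproduces its size), 127 and 254 per arm, one interim look. Assumed, because the plan gives no rule: every re-sizing rule below.

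**1. The plan's own size reproduces.**
- Fixed design: n = 2 × [2 × (1.96 + 0.8416)/0.5]² = 251.2, so 252 per arm.
- Two-look O'Brien-Fleming at half information: boundaries c1 = 2.797 and c2 = 1.977, inflation factor 1.0078. 252 × 1.0078 = 253.96, so 254 per arm.
- With the size unchanged, alpha is 0.0500 and power at 0.5 day is 80.1%.

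**2. How a size change acts.** The SE of the interim difference is 2 × √(2/127) = 0.251 day, so z1 = difference/0.251, and c1 corresponds to 0.702 day. Let r = (second-stage n per arm)/127. The pooled final test rejects in the upper tail when the second-stage z exceeds

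(1.977 × √(1 + r) − z1)/√r.

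As planned, r = 1. Suppose instead that the trial is re-powered to 80% on the observed difference d, so that final n per arm = 2 × (1.96 + 0.8416)² × 4/d², with a cap of 508:

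| Observed d (day) | z1 | Final n per arm | r | Second-stage critical z, planned → changed | Conditional false-positive rate, planned → changed |
|---|---|---|---|---|---|
| 0.2 | 0.797 | 508 (cap; formula 1,570) | 3.00 | 2.000 → 1.823 | 2.3% → 3.4% |
| 0.4 | 1.594 | 392 | 2.09 | 1.203 → 1.302 | 11.5% → 9.6% |
| 0.6 | 2.391 | 174 | 0.37 | 0.406 → −0.120 | 34.2% → 54.8% |

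An increase after a weak interim raises the error, an increase after a promising interim lowers it, and a decrease after a strong interim raises it. For increases the turning point is z1 = 1.977/√2 = 1.398, or 1.398 × 0.251 = 0.351 day. At or above it, any r > 1 lowers the conditional error.

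**3. Overall alpha.** This is the conditional rate integrated over the null distribution of z1, plus the interim crossing probability. The final test is pooled against 1.977; the size stays at 254 per arm outside the band; decreases have a floor of 128 per arm.

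| Assumed rule | Re-sizing in either sign | Re-sizing only if Anaferon is ahead |
|---|---|---|
| No change | 5.0% | 5.0% |
| Increases only, 0.25-0.5 day | 4.9% | 4.9% |
| Increases only, 0.1-0.5 day (cap 508 to 1,016 per arm) | 5.4-5.7% | 5.2-5.3% |
| Increases at any difference below 0.5 day (same caps) | 6.0-6.6% | 5.5-5.8% |
| Either direction, 0.4-0.6 day | 5.1% | 5.0% |
| Decreases only, above 0.5 day | 5.6% | 5.3% |

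**4. With the remedies.** The statistic √0.5 × z1 + √0.5 × z2, where z2 comes from second-stage patients only, tested against 1.977, gives 5.0% under every rule in the table. Increases only from 0.351 to 0.5 day, with the pooled test and cap 508, give 4.8%.

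**The case against.** **The excess may be nil.** This is the strongest objection. Minor suggests a narrow band, and both the minimum sizes in the table and the statement under Number of subjects that at least 508 should complete lean towards increases only. With increases at 0.25-0.5 day there is no inflation. That stands for that band. It does not stand for increases in general: lowering the edge to 0.1 day already gives 5.4-5.7%, and the text sets no edge.

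**Re-sizing in either sign overstates the risk.** A placebo lead of half a day is hardly a minor deviation from an expected Anaferon benefit. This is fair. The last column of the second table suits the wording better and is lower, but it still exceeds 5% under several rules.

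**The effect might include the SD.** Both quantities sit under the heading on expected effects. If re-sizing used only a blinded SD, the concern would largely fall away. The words on the achieved effect favour the group difference, but the ambiguity is real.

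**Stopping for a major deviation would offset the excess.** A binding stop would. If the trial always stopped below an assumed 0.25 day, the unchanged design would have alpha 4.1%, but its power at 0.5 day would fall from 80.1% to 74.0%. The plan words stopping as an ability and as possible, with no cut, so it cannot be credited.

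**A rule may exist elsewhere.** The document calls itself a protocol summary. That stands: the finding is about what this text specifies.

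**Conclusion.** The point holds as a gap in error control. The plan permits an effect-driven change of size without a rule or a final test that remains valid after it, so its stated alpha below 5% is not assured. The figures rest on SD 2, an interim at exactly 127 of 254 per arm, normal test statistics and assumed re-sizing rules. They range from 4.9% to 6.6% and are illustrations, not limits.

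Three other readings are tempting and unsupported:
- A reader might infer that the trial's type I error does exceed 5%. The text does not fix a rule, and some plausible rules keep alpha at or below 5%.
- A reader might infer that only decreases do harm, or that the excess is confined to about half a point. Increases after a weak interim can do more, and because the band is undefined no ceiling follows from the text.
- A reader might infer that the second look is unadjusted. Item 1.5 applies the boundary at both looks; the gap is only the data-driven size.

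**What to change.** Before the interim is unblinded, state in the SAP which quantity drives the change, the band that counts as minor, the direction and the cap. Then adopt one of these:

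- **(a) Preferred.** Make the final test an inverse-normal combination of the two stages, with weights fixed in advance at √0.5 each, against 1.977. Alpha is 5.0% under any re-sizing rule.
- **(b)** Allow increases only, and only when the interim |z| is at least 1.398 (about 0.35 day if the SD is 2). Keep the pooled test at 1.977; alpha then stays at or below 5% whatever the cap.

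These constants assume exactly half information, whereas the plan says at least 127 per group. Either fix the interim at 127 or compute boundaries, threshold and weights from the actual count before unblinding. For example, 140 of 254 per arm gives 2.673, 1.985 and 1.473, with weights √(140/254) and √(114/254). Apply them to the stage-wise standardised statistics of whichever test is used, t or Mann-Whitney. The thresholds in days apply only to the difference in means.

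**Cost.** SAP wording and a few lines of code. Power at a true 0.5 day, option (a) against the pooled test:
- Increases at 0.25-0.5 day: 86.5% v 86.3%, no loss.
- Either direction at 0.4-0.6 day: 80.1% v 80.7%.
- Either direction at 0.25-0.75 day: about 82% v 86%, a loss of 3.6 to 4 points.
- Decreases only: about 76% v 79.7%, below the planned 80%.

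Option (b) gives 82.6% (cap 508 per arm), against 86.3% if increases were allowed from 0.25 day. Part of the pooled test's advantage where decreases are allowed comes from its inflated alpha.

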14. Subjects whose parents/adoptive parents, according to the investigator's point of view, will not follow the observation requirements during the study or study product dosing regimen.
15. Participation in other clinical studies within 3 months prior to the inclusion in the study.
16. Parent/adoptive parent of the subject is related to the investigator team of medical facility directly involved in the study or is a close relative of the investigator. Close relatives include spouse, parents, children or brothers (sisters) regardless of whether they are biological or adoptive ones.
17. Parent/adoptive parent of the subject is working in OOO “NPF “Materia Medica Holding”, i.e. is the company official, temporary contract worker or an appointed official responsible for the study or their close relatives.

⁶ 1 alcohol unit – 0.33 L light beer/150 mL of unfortified wine, 40 mL of liquors.

Discontinuation criteria

1. Inability or refusal of the subject, his/her parents/adoptive parents to compliance the protocol.
2. Necessity in the medical products not allowed within the study.
3. Development of adverse event requiring the product discontinuation.
4. Subject's or parents'/adoptive parents' wish to terminate the study early due to lack of therapeutic efficacy or any other reason.
5. Cases not specified by the protocol when, according to the investigator, further subject's participation is dangerous.
6. Enrollment of ineligible subject.

Number of subjects

Signed informed consent form is supposed to be obtained from 972 subjects (of them 772 – in the Russian Federation, 100 – in Republic of Belarus and 100 – in Ukraine); this would allow to complete all protocol procedures by at least 508 subjects (n=254 in Anaferon for children and Placebo groups).

Interim analysis

An interim statistical analysis is scheduled within the study. The interim analysis will be based on the findings from examinations and therapy of the protocol-set number of subjects who completed the study. Based on the proposed effect, the minimum required Per Protocol (PP) sample size will be 254 subjects (n=127 in Anaferon for children and Placebo groups).

Treatment

Group 1

Name: Anaferon for children

Active ingredient: affinity purified antibodies to human interferon-gamma – 0.003 g*

** applied to lactose monohydrate as water-alcohol mixture containing no more than 10^{-16} ng/g of the active form of the active ingredient*

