Excipients: Lactose monohydrate 0.267 g, microcrystalline cellulose 0.03 g, magnesium stearate 0.003 g

Dosage: Per os. One tablet per intake (hold in mouth until complete dissolution – regardless of meal). The first 2 hours – every 30 minutes, then 3 additional doses with equal intervals. On days 2-5 – on tablet 3 times a day.

Dosage form: Orodispersible tablets

Description: Flat cylinder-shaped scored beveled edge white to off-white tablets

Storage conditions: Store at temperature below 25°C. Keep out of the reach of children.

Group 2

Name: Placebo

Active ingredient: NA

Excipients: Lactose monohydrate 0.267 g, microcrystalline cellulose 0.03 g, magnesium stearate 0.003 g

Dosage: Placebo using Anaferon for children scheme

Dosage form: Orodispersible tablets

Description: Flat cylinder-shaped scored beveled edge white to off-white tablets

Storage conditions: Store at temperature below 25°C. Keep out of the reach of children

Treatment period

Anaferon for children/Placebo treatment period is 5 days.

Observation period

Overall the subject is observed for 14 days (screening, randomization, treatment initiation – day 1, study therapy period – 5 days, follow-up – 1 day, phone visit – day 14).

Basic therapy

Throughout the study the subject may have symptomatic therapy of influenza/ARVI based on the accepted treatment standards including expectorants, mucolytics, vasoconstrictive nasal drops, where necessary – detoxifying therapy, as indicated* – approved antipyretics**, in case of bacterial complications of influenza/ARVI – antibacterial drugs except for antiviral, immunomodulating and other products specified in section “Prohibited concomitant therapy”.

* Indications for antipyretics products [11, 14, 34]:

Body temperature > 38.5°C;

Body temperature 38.0°C against concomitant chronic pulmonary, cardiac, nervous system diseases.

In case the antipyretic product was prescribed and given to the child by parents/adoptive parents on their own (without physician’s prescription) with no indications, the subject will not be withdrawn. Parents/adoptive parents should record temperature values in patient’s diary prior to the product administration, its name and dose.

** The products allowed as antipyretics (ATC group is specified in brackets):

1. Paracetamol (N02BE01).

2. Ibuprofen (M01AE01).

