Study design scheme

Schedule of study procedures

Procedure/Visit	Visit 1 (Day 1)	Visit 2 (Day 3)	Visit 3 (Day 5)	Visit 4 (Day 7)	Visit 5 (Day 14±1)
Obtaining signed informed consent form (ICF)	+				
Collection of complaints	+	+	+	+	
Collection of medical history	+				
Objective examination	+	+	+	+	
Recording influenza/ARVI symptoms	+	+	+	+	
Inclusion/exclusion criteria assessment	+				
Recording concomitant therapy	+	+	+	+	
Rapid test for influenza viruses in nasal swabs	+				
Obtaining nasal and oropharyngeal	+	+	+	+	

swabs for PCR diagnosis of influenza (in case of positive result of rapid test for influenza)					
Obtaining nasal and oropharyngeal swabs for PCR diagnosis of other respiratory viruses (in case of negative result of rapid test for influenza)	+				
Randomization and prescription of the study therapy	+				
Issue of the study product	+				
Issue of antipyretic product	+				
Accounting and return of the study product, determination of compliance				+	
Issue of patient's diary	+				
Revision of correctness of diary filling		+	+	+	
Diary return				+	
Therapy safety assessment		+	+	+	+
Phone contact					+

Statistical Analyses

Samples

Statistical analysis will be carried out in the following sets:

Total set – all enrolled subjects whose parents/adoptive parents had signed ICF. This set will take into account all adverse events and related conditions during the study including prior to the study therapy initiation.

Total set of the subjects receiving at least one dose of the study product will be used for safety and tolerability analysis (Safety population), as all adverse events recorded in the subject after administration of the product will be taken into account.

Full Analysis Set. This set includes all enrolled subjects excluding those having at least one of the following events:

- 1) non-compliance with inclusion/exclusion criteria;
- 2) the subject did not receive a single dose of the study product;
- 3) lack of any data on the subject after prescription of the study product

This set most fully conforming to Intention-to-treat principle will be used for Intention-to-treat analysis (ITT-analysis) of the study product efficacy.

Per Protocol set. This set includes all subjects receiving per protocol therapy in full, completing all scheduled visits and having no major deviations from the protocol. This set will be used for Per Protocol analysis (PP-analysis) of the study therapy efficacy.

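### The effect-based interim stop/resize decision is specified only on per-protocol completers, and for the final test neither the FAS nor the PP set is named primary.

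*Combined protocol and SAP*

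**What the plan says.** **Interim.** The short Interim analysis section after Number of subjects bases the look on children who completed the study and says "the minimum required Per Protocol (PP) sample size will be 254 subjects". Under Statistical Analyses, the Interim analysis section names the analysed set as "Particular Per Protocol (pPP" (pPP in short) and times the look for when "at least 127 subjects in each group complete the study, i.e. receive per protocol therapy in full", with every visit made and no major deviation. Its purposes are to adjust the sample size or to discontinue early, according to how far the observed effect departs from the planned one. Footnote 7 allows stopping for safety, for lack of efficacy, or "after the required power of statistical efficacy conclusions is achieved". Evaluation of sample size and Statistical criteria both set an O'Brien-Fleming boundary. No FAS interim is described.

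**Leaving the set.** The Discontinuation criteria include an adverse event, need for a disallowed product, and a family's wish to "terminate the study early due to lack of therapeutic efficacy or any other reason". Basic therapy narrows these exits. Symptomatic drugs, listed antipyretics and antibacterials for complications are permitted, and if an antipyretic is given "with no indications, the subject will not be withdrawn".

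**Final.** The Samples section describes the FAS with the words "This set most fully conforming to Intention-to-treat principle" and says it "will be used for Intention-to-treat analysis (ITT-analysis) of the study product efficacy". The PP set gets its own efficacy analysis in the next paragraph. Neither is called primary. The 508 in Evaluation of sample size counts per-protocol completers.

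**The concern.** A superiority comparison is protected by randomisation only while children are compared as randomised. Full therapy, complete visits and absence of major deviations are all known only after treatment starts, and some exits are related to how the illness goes. An FAS analysis could still be run after an interim stop, but the decision would already have been taken.

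At the final, the plan leaves open which set answers the trial's question. If one set is significant and the other is not, the choice would be made with results in hand.

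Two further wordings matter once the FAS is asked to carry the primary test. Its first exclusion, as written, removes randomised children later found ineligible, a case the Discontinuation criteria foresee. And last observation carried forward fills visit values. It does not say what illness duration belongs to a child who leaves before recovery or improvement.

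**Working it through.** **Inputs from Evaluation of sample size:** difference 0.5 days (worded as less than 0.5), SD 2 days, two-sided 5%, power 80%, one interim and one final look, 127 then 254 PP children per arm, withdrawal coefficient 0.4774.

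**The plan's own figures reproduce.**
- Fixed design: 2 × [2 × (1.960 + 0.842)/0.5]² = 251.2 per arm.
- O'Brien-Fleming, two looks at half and full information: final value 1.977, interim 1.977 × √2 = 2.797 (nominal two-sided p 0.048 and 0.0052). The inflation factor of 1.0078 gives 253.1 per arm; the plan has 254, with 127 at the interim. Overall power with 254 is 80.1%.
- Enrolment: 508/(1 − 0.4774) = 972.06; the plan has 972.

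**How often the interim decides.** SE = 2 × √(2/127) = 0.251, so the expected Z is 0.5/0.251 = 1.99. P(Z > 2.797 − 1.99) = 21.1%. As a share of all successes: 21.1/80.1 = 26%.

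**How often the two sets differ.** The documents do not give the FAS size, because the 0.4774 mixes screening failures with later loss. Assumptions: a share f of FAS children, 10% or 20%, is outside PP for reasons unrelated to outcome and keeps a share k of the effect, from none to all.
- FAS per arm = 127/(1 − f) at the interim (141 or 159) and 254/(1 − f) at the final (282 or 318).
- FAS effect = 0.5 × (1 − f + f·k).
- The two Z values are bivariate normal with correlation √(1 − f) = 0.949 or 0.894, since PP is nested in the FAS.
- Example, f = 10%, k = 0: effect 0.45, SE 2 × √(2/141.1) = 0.238, expected FAS Z 1.89 against 1.99 for pPP.

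| f | k | Interim: pPP alone crosses | Interim: FAS alone crosses | Final: sets disagree | FAS power, two looks |
|---|---|---|---|---|---|
| 10% | 0 | 5.1% | 2.3% | 8.4% | 75.9% |
| 10% | 0.5 | 3.7% | 3.7% | 7.2% | 80.2% |
| 10% | 1 | 2.4% | 5.7% | 7.4% | 84.1% |
| 20% | 0 | 8.1% | 2.6% | 13.9% | 70.9% |
| 20% | 0.5 | 5.2% | 5.5% | 10.2% | 80.6% |
| 20% | 1 | 2.8% | 10.2% | 11.0% | 88.1% |

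Interim percentages are of all trials. The final column takes each trial as running to 254 PP per arm and counts those where exactly one set exceeds 1.977.

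**Outcome-related loss that is equal by arm.** This was simulated with a null drug, a normal outcome, a probability of leaving that rises with illness duration (logistic slope 1 or 2 per SD), 10% or 20% lost in both arms, and 60,000 trials per case. The PP test rejects in 0.55-0.60% at 2.797 (t-test nominal 0.56%) and 4.8-4.9% at 1.977 (nominal 4.85%). Error stays about nominal.

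Unequal outcome-related loss was not calculated, because the documents give no basis for its size or direction.

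**The case against.** The best defence has four parts.

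- **The FAS is primary by implication, because the plan calls it closest to intention-to-treat.** That wording describes the set; it does not designate it. Equally, counting 254 and 508 on PP children does not make PP primary, since it may only secure enough evaluable children. Neither inference is supported.
- **This is a protocol summary, and a fuller text may name the set.** That stands as a limit. The absence is certain only for this document. The interim half does not depend on it, because the pPP set is stated outright.
- **No harm is shown.** Much of this stands. A reader might infer that a completers-only interim inflates false positives. The documents do not support that: equal loss leaves error about nominal, and inflation would need unequal outcome-related loss, for which they give no figure. Basic therapy also closes some of the exits.
- **The disagreement runs both ways.** This stands too. With 10% outside PP and half the effect kept, each set crosses alone in 3.7% of trials. With the full effect kept, the FAS crosses alone more often than pPP. It would be wrong to read the pPP-only crossings as surplus or false stops, since a true 0.5-day effect is assumed throughout.

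A reader might also infer that success may be claimed on either set. That would put two-sided error at the final look at 6.2-6.8% against 4.8%, but the plan states no such rule.

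**Conclusion.** The concern holds as a gap in pre-specification, not as demonstrated bias and not as an arithmetic error. The only look that can stop or resize the trial on effect is specified on a set selected after randomisation. At the final, this document neither names a primary set nor says what happens when the two conflict.

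On the plan's figures about 26% of successful trials would be decided on pPP. On the assumed 10% or 20% outside PP, with none to all of the effect kept, pPP alone crosses at the interim in 2.4-5.1% or 2.8-8.1% of trials, and the FAS alone in 2.3-5.7% or 2.6-10.2%. At the final the sets disagree in about 7-8% or 10-14%. These figures depend on the assumed share outside PP, on loss unrelated to outcome and on the plan's effect being true. They measure how often the choice of set would matter, not an error rate.

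**What to change.** - Name the FAS, analysed as randomised, as the primary efficacy set for both the interim boundary test and the final test, with pPP and PP supportive.
- Compute the O'Brien-Fleming boundaries at the FAS information fraction actually reached. If that is 0.50, as with 141 of 282 per arm, they remain 2.797 and 1.977.
- Limit the first FAS exclusion to breaches of objective pre-randomisation criteria, judged blind to treatment and outcome.
- State in advance what illness duration is assigned to a child who leaves before recovery or improvement.
- Restate the 80% power for the FAS.

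The cost is text only, with no extra enrolment if the restated power is accepted. With 508 PP children, FAS power is about 76-84% if 10% of FAS children are outside PP (FAS 564) and 71-88% if 20% are (FAS 635). It falls below 80% if those children keep less than about half the effect. Holding 80% in the worst case, with no effect kept, would need about 254/0.9² = 314 FAS children per arm instead of 282, or 254/0.8² = 397 instead of 318.
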